Study Protocol

Study Title:

To investigate the potential effectiveness of mirror-aided cross-education using the innovative 'Mirror Strengthening Device' compared to mirror therapy alone in post-stroke upper limb recovery: A pilot randomised feasibility study.

Document creation date: February 4th 2022

NCT number [not yet assigned].

Identifiers: [NCT ID not yet assigned]

Study Protocol

To investigate the potential effectiveness of mirror-aided cross-education using the innovative 'Mirror Strengthening Device' compared to mirror therapy alone in post-stroke upper limb recovery: A pilot randomised feasibility study.

Study Objectives:

1. To conduct a randomised controlled pilot feasibility study to examine the effects of mirror-aided cross-education using a specially designed Mirror Strengthening Device in post stroke upper limb recovery.
2. To examine the feasibility of mirror-aided cross-education using a specially designed Mirror Strengthening Device in this patient cohort
3. To investigate any adverse effects of mirror-aided cross-education using a specially designed Mirror Strengthening Device in this population.

Study Design:

The Design is an assessor blinded, randomised control pilot feasibility trial. The independent assessor, who is blinded to the treatment assignment, will perform all the assessments. After baseline measurements are obtained, the patients will be randomly assigned to the intervention or control group using computer generated block random numbers where gender and function will be considered. A statistician who will be blinded to the research protocol and not otherwise involved in the trial will conduct the random number programme.

Setting:

Assessments: Exercise Physiology Lab, IT Sligo.

Intervention: Participants own home.

Intervention:

Both groups will perform a 5 minute warm up, 5 minute cool down and main set of exercises consisting of up to 4 sets of 5 repetitions of 5 dynamic shoulder exercises.

They will be instructed to perform the concentric and eccentric phases of the contraction at 3 seconds and 4 seconds, respectively, rest for 2 sec between contraction and rest between sets. The full set should take approximately 30mins.

Participants will be asked to complete the intervention 5 days a week for 4 weeks.

Experimental Group:

The experimental group will be performing the repetitions with a set resistance on the Mirror Strengthening Device

Control Group:

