The control group will be performing the repetitions with no resistance on the Mirror Strengthening Device.

Positioning:

Participants will be seated in a chair in front of their own kitchen table. The elbow is flexed at 90 degrees and kept in close to the trunk not resting on anything. Palm of hand is facing the exercise device and holding a pulley. The untrained limb will be positioned in a similar position to the training limb supported on the table behind the exercise device with the shoulder slightly flexed forward to allow this positioning.

Participants will view the mirror reflection of their less- affected limb in the mirror which is positioned lateral to the mid-sagittal plane of the more - affected limb before any strength training commences.

The participant will be asked to look at the reflected image of their less-affected limb in the mirror as they train. They will then complete the prescribed HEP.

Rests:

Participants will be informed that breaks can be taken during the training session for reasons of tiredness or fatigue if required.

Training Diary:

All participants will be provided with a training diary. They will be asked to completed this before and after each training session.

Adverse Effects:

All participants will be asked to record any changes before and after each training session in the HEP record book and to contact Principal Researcher with any adverse effects.

Outcome Assessments:

Outcome Measures will be taken before and after the 4-week home exercise programme and at 3 months follow up and will include:

Primary:

Isokinetic Strength: (Biodex System 4 Pro with advantage software)

Grip Strength: (Hand held dynamometer)

Secondary:

Fugl-Meyer Upper Extremities Test

Stroke Impact Scale

Modified Ashworth Scale (MAS) for spasticity).

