## Statistical Analysis

We will analyse the data using Excel and SPSS for Windows. Paired T tests will be used to compare before and after data in both groups.

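### The primary strength outcomes name no limb and are tested only before against after, so the plan does not separate direct training of the exercised limb from cross-education

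*Protocol*

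**What the plan says.** Under Outcome Assessments, the protocol lists two primary outcomes: "Isokinetic Strength: (Biodex System 4 Pro with advantage software" and "Grip Strength: (Hand held dynamometer". Each entry names an instrument. Neither names a limb, joint, movement, test speed or summary parameter. Measurements are planned at baseline, after the 4-week programme and at 3 months, and none of these is named as the primary time point.

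The Positioning section shows which limb does the work. While exercising, each participant is asked to "look at the reflected image of their less-affected limb in the mirror as they train". The other limb rests: "The untrained limb will be positioned in a similar position to the training limb supported on the table behind the exercise device".

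The arms differ in load. Under Intervention, the experimental group is "performing the repetitions with a set resistance on the Mirror Strengthening Device", while controls do the same repetitions on the same device unloaded.

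The SAP's Statistical Analysis section gives one analysis: "Paired T tests will be used to compare before and after data in both groups". It names no limb and no test between the arms.

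**The concern.** In this design the choice of limb decides which question is answered. Strength in the less-affected limb shows whether resistance training strengthens the muscles that were trained. Strength in the more-affected limb can show whether anything crossed over, which is what the title and first objective set out to study. The primary outcome entries fit either limb.

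The planned test does not settle the matter. A before/after comparison within the experimental arm picks up any cause of change over 4 weeks. On the exercised limb, direct training is the obvious one. On the more-affected limb, the test would still mix transfer from resisted exercise with everything both arms share: the mirror exposure, familiarity with the test, and any natural recovery.

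At stake is what the pilot can be said to have shown. A strength gain that reflects ordinary training could be read as a sign that cross-education works, and could be used to justify a larger trial.

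**Working it through.** **Step 1. What each possible analysis would measure.** The documents state no sample size, power, significance level, effect size or SD, so there is no figure of the plan's own to reproduce. The main check is to set limb against comparison.

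| Limb measured | Before/after within the experimental arm | Between randomised arms |
|---|---|---|
| Less-affected (trained) | Direct training plus any other change over time | Direct effect of resistance |
| More-affected (untrained) | Transfer from resisted training, mirror exposure, test familiarity and natural recovery, all together | Added effect of resistance carried to the untrained limb |

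Only the lower right cell matches a trial of resisted mirror training against mirror therapy alone. The visible plan fixes the left-hand column and leaves the row open. Both parts therefore need changing. Naming the limb without the comparison leaves the lower left cell, and adding the comparison without the limb still allows the upper right.

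**Step 2. How easily direct training alone could give a significant paired test (illustration only).** Assumptions, none of them from the documents:

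- two-sided 5% test, counting significant improvements only;
- n = 8, 10, 15 or 20 in the experimental arm;
- true mean gain in the trained limb of d = 0.5, 0.8 or 1.0, in units of the SD of change;
- zero cross-education.

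The probability is P(T > t₀.₉₇₅,ₙ₋₁), where T is noncentral t with n − 1 degrees of freedom and noncentrality d√n. For n = 8 the noncentrality is 0.5 × √8 = 1.41 at the low end and 1.0 × √8 = 2.83 at the high end. For n = 20 it is 0.5 × √20 = 2.24 and 1.0 × √20 = 4.47.

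| n in arm | d = 0.5 | d = 0.8 | d = 1.0 |
|---|---|---|---|
| 8 | 0.231 | 0.496 | 0.681 |
| 10 | 0.293 | 0.616 | 0.803 |
| 15 | 0.438 | 0.821 | 0.949 |
| 20 | 0.564 | 0.924 | 0.989 |

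If the same test is applied to the untrained limb, with no cross-education and no other change over time, the chance of a significant improvement is 0.025.

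**Step 3. Would a test between arms be enough by itself?** No. This test is not in the visible plan, so the figures show only why the limb must also be named. Let the arms differ by d SD in change on the trained limb. The noncentrality is then d√(n/2) with 2n − 2 degrees of freedom. For d from 0.5 to 1.0, the chance of a significant difference favouring the experimental arm is 0.152 to 0.461 at 8 per arm and 0.338 to 0.869 at 20 per arm, still with zero cross-education. Here d is the difference between arms. If controls also gain from unloaded repetitions, it is smaller than the experimental arm's own change in Step 2, so the two sets of figures should not be matched row by row.

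**The case against.** The strongest reply is that the intended limb is evident. The title and objectives are about cross-education and, in the title and first objective, post-stroke upper limb recovery. The Positioning section keeps the training limb and the untrained limb apart. Presenting a trained-limb gain as cross-education would contradict the protocol's own aim. This stands as far as intent goes. A reader might infer that the trial will measure the wrong limb, and the documents do not support that.

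A reader might also infer that a trained-limb gain would formally count as primary success. That goes too far as well. The visible text has no success criterion, hypothesis or decision rule, and the study calls itself a pilot feasibility study with feasibility and adverse effects among its objectives. The text fails to exclude a reading, which is weaker than adopting it.

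Three further limits stand. Part of the SAP was not available for this review, so its silence on the limb can be asserted only of the text that was. The mechanism is weaker for grip, since the programme consists of shoulder exercises with the hand holding a pulley. And missing joint, speed and torque parameter would, taken alone, be no more than missing detail.

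What the reply does not remove is that no visible sentence turns the aim into an outcome definition, and that the one stated analysis could not isolate cross-education even if the limb were agreed. Pilot status does not excuse this: strength is labelled primary, and examining effects is the first objective.

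**Conclusion.** The point holds as a gap in both outcome definition and analysis. As written, the primary strength outcomes can be met by either limb, and the visible analysis tests change over time and not the difference that randomisation creates. Together they do not separate direct training from cross-education.

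The size cannot be fixed from the documents. Under the stated assumptions, direct training alone makes the experimental arm's paired test on the trained limb significant in about 23–68% of trials at 8 per arm and 56–99% at 20 per arm. These figures depend wholly on the assumed sample size and on an effect of 0.5 to 1.0 SD of change. They show that the ambiguity could matter and do not forecast this trial's error rate. The conclusion itself rests on the layout in Step 1 and needs no assumed numbers. It is subject to whatever the unavailable part of the SAP says.

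**What to change.** Define both primary strength outcomes as those of the untrained, more-affected limb: isokinetic strength at that shoulder and grip in that hand. The investigators should fix the shoulder movement, test speed, torque parameter and primary time point in writing before any data are seen.

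Replace the within-group paired t-tests, as the primary analysis, with a comparison between randomised arms adjusted for the baseline value. ANCOVA would do this: follow-up value = intercept + arm effect + slope × baseline value + error, reporting the arm effect with its confidence interval. Within-group changes can remain as description. Report less-affected-limb strength separately, as a check that training worked and not as evidence of cross-education.

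The change uses outcomes and visits already planned and leaves the interventions as they are. It has two costs. Trained-limb gains and other torque readings can no longer be presented as primary results. And some participants may have floor or missing readings on the more-affected limb. Their number should be reported by arm, together with how they were handled, which is useful feasibility information in its own right.

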## Statistical Analysis

We will analyse the data using Excel and SPSS for Windows. Paired T tests will be used to compare before and after data in both groups.

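### The only analysis named is a paired t-test within each arm, so the randomised comparison of resistance with no resistance is never made

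*SAP*

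**What the plan says.** The Protocol sets up a comparison. Its title asks about the device "compared to mirror therapy alone in post-stroke upper limb recovery". Under Study Design it states: "The Design is an assessor blinded, randomised control pilot feasibility trial". Allocation follows the baseline measurements: "the patients will be randomly assigned to the intervention or control group using computer generated block random numbers", with gender and function taken into account. Objective 1 is "To conduct a randomised controlled pilot feasibility study to examine the effects of mirror-aided cross-education".

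Under Intervention, both arms share the warm-up, cool-down and main exercises, 5 days a week for 4 weeks. Both use the device. For the experimental arm, "The experimental group will be performing the repetitions with a set resistance on the Mirror Strengthening Device"; the control arm does the repetitions without resistance. Outcomes are measured before the programme, after it, and at 3 months. Isokinetic strength and grip strength are primary.

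The SAP's Statistical Analysis section has two sentences. The first names the software: "We will analyse the data using Excel and SPSS for Windows". The second names the method: "Paired T tests will be used to compare before and after data in both groups". No between-arm test, model, estimate or interval appears in either document as supplied.

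**The concern.** A paired t-test in one arm estimates the total change in that arm. That total mixes several things:

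- any effect of resistance;
- the effect of the exercise programme both arms perform;
- recovery over the 4 weeks;
- practice from repeat testing on the dynamometers;
- regression to the mean, if participants are selected for weakness.

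Randomisation exists to remove everything on this list except the first, and it does so only through a contrast between arms. With two separate paired tests, treatment arm never enters the analysis.

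The likely consequence is that the two p-values are compared informally, and a significant change in the experimental arm beside a non-significant one in the control arm is taken as evidence for resistance. That is not a test of the difference. The reverse error is also possible: if both arms improve significantly, a real advantage for one of them goes unmeasured. Either way, the pilot would not report the between-arm estimate and interval that objective 1 and the planning of a later trial call for.

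**Working it through.** **Inputs.** The documents give no sample size, alpha, effect size or SD, so there is no planned figure to reproduce. Everything below is an assumption, chosen to show scale:

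- two-sided alpha of 0.05 for each test;
- n per arm from 8 to 30;
- the same true standardised mean change, dz (mean change divided by SD of change), of 0.3, 0.5 or 0.8 in both arms, so the true between-arm difference is zero;
- independent arms with normally distributed changes.

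**Step 1: chance that one arm shows significant improvement.** The paired t statistic follows a non-central t distribution with n − 1 degrees of freedom and non-centrality dz × √n. So p = P(T > t(0.975, n − 1)).

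For n = 15 and dz = 0.5, the critical value is 2.145 and the non-centrality is 0.5 × √15 = 1.936, giving p = 0.438.

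**Step 2: chance of each pattern.** With independent arms and equal true change:

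- experimental significant, control not: p(1 − p) = 0.438 × 0.562 = 0.246;
- exactly one arm significant: 2p(1 − p) = 0.492;
- both significant: p² = 0.192.

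**Step 3: range over the assumptions.**

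| n per arm | dz | p, one arm | Experimental only | Exactly one arm |
|---|---|---|---|---|
| 8 | 0.3 | 0.111 | 0.099 | 0.197 |
| 8 | 0.8 | 0.496 | 0.250 | 0.500 |
| 10 | 0.5 | 0.293 | 0.207 | 0.414 |
| 15 | 0.3 | 0.190 | 0.154 | 0.308 |
| 15 | 0.5 | 0.438 | 0.246 | 0.492 |
| 15 | 0.8 | 0.821 | 0.147 | 0.294 |
| 20 | 0.5 | 0.564 | 0.246 | 0.492 |
| 20 | 0.8 | 0.924 | 0.070 | 0.141 |
| 30 | 0.5 | 0.754 | 0.186 | 0.371 |
| 30 | 0.8 | 0.988 | 0.011 | 0.023 |

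For 8 to 20 per arm, the experimental-only pattern occurs in 7% to 25% of trials and exactly one arm is significant in 14% to 50%. Extending to 30 per arm lowers the bottom of these ranges to about 1% and 2%. In that corner both arms are almost always significant, which still says nothing about the difference between them.

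**Step 4: a valid comparison under the same conditions.** In 100,000 simulated trials per scenario (n of 10, 15, 20 and 30; dz of 0.5 and 0.8), a two-sample t-test on change scores was significant in 4.9% to 5.1%. A two-sided 5% test favours the experimental arm in half of those, 2.5%. The simulation also reproduced the paired-test results, for example 0.437, 0.245 and 0.493 at n = 15 and dz = 0.5.

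**Step 5: which between-arm analysis.** Let ρ be the correlation between baseline and post-programme values, with equal variances. Relative to comparing post-programme values alone (variance 1), a change-score comparison has variance 2(1 − ρ) and ANCOVA has 1 − ρ². The ratio of ANCOVA to change score is (1 + ρ)/2.

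| ρ (assumed) | ANCOVA | Change score | ANCOVA ÷ change score |
|---|---|---|---|
| 0.5 | 0.75 | 1.00 | 0.75 |
| 0.7 | 0.51 | 0.60 | 0.85 |
| 0.9 | 0.19 | 0.20 | 0.95 |

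Both are valid. ANCOVA is the more precise, and the gain shrinks as ρ approaches 1.

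**The case against.** The strongest reply is that this is a pilot feasibility study. Two of its three objectives concern feasibility and adverse effects, and no powered hypothesis test is owed. That is right, but it argues for estimation rather than for testing the wrong contrast. The SAP does plan significance tests, and objective 1 is comparative. For scale, 80% power to detect a between-arm difference of 0.5 or 0.8 SD would need about 63 or 25 per arm, so a wide interval is to be expected and should be reported as such.

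Other points stand in part:

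- Part of the SAP was not available for review, so 'only' means the only analysis named in the text supplied. Nothing in that text points to a between-arm analysis elsewhere, and the sentence on paired tests needs correcting in any case.
- The information is not destroyed. Each paired test yields a mean change and an SD of change, from which a reader could work out a difference and a pooled SD. The defect is that the plan does not commit to that contrast.
- The SAP does not say that a mixed pair of p-values will be read as efficacy. The 25% measures a foreseeable misreading, not a stated decision rule. It also sits almost at the mathematical maximum of p(1 − p), so it is close to a worst case.
- Both arms use the device, so the untested contrast is strictly set resistance against none.

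None of these supplies the missing comparison.

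**Conclusion.** The concern holds and must be fixed. The stated analysis cannot answer the comparative part of the title or objective 1, because it cannot separate the effect of resistance from improvement shared by both arms. This follows from what a paired t-test is and depends on no assumed number.

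The numerical illustration does rest on assumptions: sample size, equal true change in the two arms, normality and independence. Within them, reading two paired tests side by side would suggest a non-existent advantage for resistance in up to a quarter of trials, or about ten times the 2.5% of a proper comparison (0.246 ÷ 0.025 = 9.8). The excess disappears only where the shared improvement is large and the arms are at the top of the range considered.

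**What to change.** Replace the sentence on paired tests with text such as:

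> For each strength outcome, the primary analysis compares experimental with control at the end of the 4-week programme by ANCOVA, with the post-programme value as outcome and arm and baseline value as covariates. The adjusted mean difference is reported with its 95% confidence interval, with participants analysed as randomised. Within-group changes are descriptive only.

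Two refinements are worth settling at the same time. If gender and function were used as randomisation factors, add them to the model. State also whether the 3-month values will be analysed in the same way as a secondary comparison.

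The cost is SAP wording. Baseline is already measured before randomisation, and ANCOVA is standard in SPSS, which the SAP already names. No further participants or data are needed. The one drawback is that the interval will be wide, which is an honest reflection of what a pilot can show.

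### The 3-month assessments have no stated analysis, so any conclusion on whether a gain is kept would be post hoc

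*SAP*

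**What the plan says.** Under Outcome Assessments the protocol sets the schedule: "Outcome Measures will be taken before and after the 4-week home exercise programme and at 3 months follow up". It applies to two primary outcomes (isokinetic strength and grip strength) and three secondary outcomes (the Fugl-Meyer upper-limb test, the Stroke Impact Scale and the Modified Ashworth Scale). Under Intervention it fixes the length of the programme: "Participants will be asked to complete the intervention 5 days a week for 4 weeks".

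Under Statistical Analysis the SAP names Excel and SPSS and gives one method: "Paired T tests will be used to compare before and after data in both groups". The available text does not mention the 3-month visit, a primary time point, a contrast between the two follow-up visits or a repeated-measures analysis. The protocol does not say whether 3 months is counted from baseline or from the end of the programme.

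**The concern.** A paired t test takes two values per person, and the schedule produces three. One visit is therefore left out unless the plan says how it is used, and the plan does not.

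The first study objective is to examine effects on upper-limb recovery after stroke. Prescribed training stops at 4 weeks. The 3-month visit is the only assessment that can separate a change seen at the end of training from one that lasts. Participants undergo a third full assessment, yet nothing states how those results will be summarised or what they will be compared with. A retention result chosen after the data are seen carries less weight than one planned in advance.

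**Working it through.** The documents give no sample size, significance level or power for this point, so there is no figure of theirs to reproduce. The check sets the visit schedule against the stated analysis.

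**Inputs**
- Visits: 3 (protocol, Outcome Assessments).
- Outcomes: 2 primary + 3 secondary = 5 (same section).
- Programme length: 4 weeks (protocol, Intervention).
- Analysis: a paired t test within each group (SAP, Statistical Analysis).

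**Step 1: contrasts available.** Three visits give 3 × 2 / 2 = 3 pairwise contrasts per outcome and group. One paired test covers 1 of the 3.

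**Step 2: what each reading of the SAP sentence covers.**

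| Follow-up value used | Before v week 4 | Before v 3 months | Week 4 v 3 months | Visit left unused |
|---|---|---|---|---|
| End of programme | yes | no | no | 3 months |
| 3 months | no | yes | no | end of programme |
| Each follow-up in turn | yes | yes | no | none |

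The first row is the natural reading. The SAP repeats the before-and-after pairing that the protocol ties to the 4-week programme, and the protocol adds 3 months as a separate item. No row contains the week 4 v 3 months contrast, which addresses retention directly. No row compares the arms either, because a paired test compares two values from the same person.

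**Step 3: size on the natural reading.** Counting one score per instrument:
- Scheduled measurements per participant: 5 × 3 = 15.
- Used by the stated analysis: 5 × 2 = 10.
- No stated use: 15 − 10 = 5, and 5 / 15 = one third.

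This counts the schedule and assumes full attendance. If an instrument gives several scores, the share is still one third, since every outcome is measured at every visit.

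**Step 4: the undefined start of the 3 months.** Take 3 months as 52 / 4 = 13 weeks, and assume the programme starts at baseline.
- Counted from baseline, the gap after training is 13 − 4 = 9 weeks.
- Counted from the end of the programme, it is 13 weeks.

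The interval over which retention is judged therefore differs by 4 weeks between the two readings.

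**The case against.** The strongest reply is that this is a pilot feasibility study. None of its three objectives mentions durability, and the 3-month data will be collected and can be summarised whatever the SAP says. That stands in part. A reader might infer that the trial will be unable to say whether a gain is kept, but the documents do not support that: the data will be there, and what is missing is a plan for them. The importance of retention is inferred from the aim of studying recovery and from the decision to schedule the visit at all.

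A reader might also infer that the follow-up value could be either visit, so that the more favourable one could be chosen as the headline. The SAP does not define the term and no primary time point is named, so some looseness exists. It is minor, because the protocol's own wording points to the end of the programme. Running the test at each follow-up is also possible, though nothing says so.

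Nor do the documents support turning that looseness into a false-positive rate. This would need the looser reading, independent tests and a significance level of 0.05, which is stated nowhere. Two primary outcomes at one fixed visit would already give 1 − 0.95² = 9.75% under the last two assumptions, so much of any such figure would come from having two primaries. Repeated strength measures on the same people are also likely to be correlated, which would lower it.

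Finally, a single repeated-measures model is not the only remedy. No sample size is available to show that it could be supported, and it does not suit the ordinal Modified Ashworth Scale.

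**Conclusion.** The point holds as an omission. On the natural reading, one of three scheduled visits has no stated analysis, and none of the readings considered includes the contrast between the end of training and 3 months. Any retention finding would be post hoc. The conduct of the trial is not invalidated, and the gap is cheap to close, so this is a change the team should make.

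The conclusion rests on reading the SAP's before-and-after wording in the protocol's sense, and on the SAP text available. Part of the SAP was not available and could contain more, so confidence is moderate.

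**What to change.** Amend the SAP as follows:

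- Name the end of the 4-week programme as the primary time point and 3 months as a pre-specified secondary time point.
- State whether 3 months runs from baseline or from the end of the programme.
- For the continuous outcomes, report the baseline-adjusted between-arm difference with a 95% CI at each follow-up visit. ANCOVA per visit is enough: value at visit = intercept + slope × baseline value + arm effect + error, where the arm effect is the difference to report. A repeated-measures model is an alternative if the sample size supports it.
- Report the change from week 4 to 3 months by arm, with its 95% CI for the continuous outcomes.
- Use an ordinal or descriptive summary for the Modified Ashworth Scale.

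The between-arm estimate goes further than naming the visits. It is included because the stated paired tests make no use of the randomised comparison at any visit, and the data for it are already scheduled.

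The cost is SAP wording and a little more work in SPSS, which the SAP already names. No new visits or data are needed. The team gives up the freedom to choose the headline time point.

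### The available SAP text plans only within-arm before-and-after tests and commits to no between-arm estimate or confidence interval, although the randomised pilot asks how the device compares with mirror therapy alone

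*SAP*

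**What the plan says.** The SAP's Statistical Analysis section, as available, has two sentences. One names the software: "We will analyse the data using Excel and SPSS for Windows". The other names the method: "Paired T tests will be used to compare before and after data in both groups". No comparison of the two arms, effect estimate, confidence interval or significance level is mentioned. Some SAP text was removed before review, so this describes the available text only.

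The protocol sets a comparative question. Its title begins "To investigate the potential effectiveness of mirror-aided cross-education" and continues "using the innovative 'Mirror Strengthening Device' compared to mirror therapy alone in post-stroke upper limb recovery". Study Design states: "The Design is an assessor blinded, randomised control pilot feasibility trial". The first objective is "To conduct a randomised controlled pilot feasibility study to examine the effects of mirror-aided cross-education".

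The control is active. Under Intervention, both arms have the same warm-up, cool-down and shoulder exercises on the same schedule. The difference is resistance: "The control group will be performing the repetitions with no resistance on the Mirror Strengthening Device". Outcome Assessments lists two primary measures (isokinetic strength and grip strength) and three secondary ones, taken at baseline, after the 4-week programme and at 3 months.

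**The concern.** A paired t test compares each person with himself or herself. Run separately in each arm, it asks whether that arm changed. It cannot ask whether one arm changed more than the other, which is what randomisation was set up to answer.

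Two consequences follow if the sentence is carried out as written.

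- **False reassurance.** Exercise, practice at the assessments or natural recovery can move both arms. A significant change in the resistance arm could then be reported as a benefit of resistance when the control arm improved just as much. Significance in one arm and not the other could be read as a difference between arms that was never estimated.
- **Hidden uncertainty.** A pilot's result on potential effectiveness is useful only if the reader can see how wide a range of added effects the data allow. Within-arm tests do not show that range.

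**Working it through.** The available text states no sample size, SD, effect, significance level or power, so there is no figure of the plan's own to reproduce. What follows is illustration under assumptions: a two-sided 5% level, 1:1 allocation, and equal SD of change in the two arms.

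**Step 1: what the stated test does when resistance adds nothing.** Let dz be the true mean change divided by the SD of change. Within one arm of n people, the paired t statistic has n − 1 degrees of freedom and noncentrality dz × √n. Power is the chance that it passes the two-sided 5% critical value. Assume both arms improve equally with dz = 0.8, so the true arm difference is zero.

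| n per arm | noncentrality | power in each arm (p) | both arms significant (p²) | resistance arm only (p(1 − p)) |
|---|---|---|---|---|
| 10 | 0.8 × 3.162 = 2.53 | 0.62 | 0.62² = 0.38 | 0.62 × 0.38 = 0.24 |
| 15 | 0.8 × 3.873 = 3.10 | 0.82 | 0.82² = 0.67 | 0.82 × 0.18 = 0.15 |
| 20 | 0.8 × 4.472 = 3.58 | 0.92 | 0.92² = 0.85 | 0.92 × 0.08 = 0.07 |

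With a smaller common improvement, dz = 0.5, p is 0.29, 0.44 and 0.56. The chance that only the resistance arm is significant is then 0.21, 0.25 and 0.25. An analysis that compared the arms directly at the 5% level would point in favour of resistance in only 2.5% of such trials.

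**Step 2: how uncertain the arm difference would be.** In units of the SD of change, the 95% half-width for the difference in mean change is t(0.975, 2n − 2) × √(2/n). For the mean change within one arm it is t(0.975, n − 1) / √n.

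| n per arm | between-arm half-width | within-arm half-width |
|---|---|---|
| 10 | 2.101 × 0.447 = 0.94 | 0.72 |
| 15 | 2.048 × 0.365 = 0.75 | 0.55 |
| 30 | 2.002 × 0.258 = 0.52 | 0.37 |

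The interval that answers the title's question is wider than the within-arm one: 0.94 / 0.72 = 1.31 times at 10 per arm.

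**Step 3: units.** These are SDs of change, not SDs of the outcome. The two are linked by SD of change = outcome SD × √(2(1 − ρ)), where ρ is the baseline-to-follow-up correlation, which is not given. If ρ were 0.5 the two are equal. If ρ were 0.8 the factor is √0.4 = 0.63, and 0.94 and 0.75 become about 0.59 and 0.47 outcome SDs.

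**The case against.** The case for leaving the text alone has four parts.

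- **A paired t test already yields estimates.** It is calculated from the mean change and its SD, and the named software prints both. A reader might infer that the plan produces no estimate at all; that would be too strong. What stands is that the available text does not commit to reporting estimates with intervals. It also names no arm difference, which a within-arm test does not supply.
- **Low power has not been shown.** A reader might infer that a pilot with no stated power will probably end non-significant even if the device works. The documents do not support that, because sample size, SD and effect are not given. For the stated paired test at 10 per arm, power runs from 9% (effect 0.2 outcome SD, ρ = 0.5) to 94% (0.8 outcome SD, ρ = 0.8). Even for a between-arm test, which the SAP does not state, power at 10, 15 and 30 per arm is 19%, 26% and 48% for 0.5 SD of change, and 40%, 56% and 86% for 0.8 SD. In two of those six cases significance is the likelier result.
- **Text is missing.** The removed SAP text may contain a sample size, a between-arm analysis or a reporting rule. This stands, so the point is confined to the available text.
- **The study's purpose is not stated to be sizing a later trial.** This also stands. The word pilot suggests that purpose, but the objectives cover effects, feasibility and adverse effects. A rule for planning a later trial, or a ban on all p-values, would therefore go beyond what the documents justify.

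None of these replies meets the main point: the title and design pose a between-arm question, and the one stated method is within-arm.

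**Conclusion.** The concern holds for the available SAP text. The single stated method does not estimate the comparison in the title, and no between-arm estimate or confidence interval is promised. Because both arms train on the device, significant before-and-after changes can appear in both when resistance adds nothing. Under an equal improvement of dz = 0.8, the chance that both are significant is about 38% to 85% at 10 to 20 per arm.

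The size of the uncertainty left unreported is illustrative only: half-widths of about 0.94, 0.75 or 0.52 SDs of change at 10, 15 or 30 per arm. It rests on assumed sample sizes, 1:1 allocation and equal SDs. Power cannot be judged either way. The conclusion about the choice of comparison does not depend on any of these assumptions.

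**What to change.** Replace the paired-test sentence in the SAP's Statistical Analysis section with a statement to this effect: for each primary and secondary outcome, at 4 weeks and at 3 months, the mean change from baseline and the SD of change will be reported for each arm, together with the between-arm difference in mean change and its 95% confidence interval. The conclusion about the device will rest on that difference and interval, not on within-arm p-values.

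If the SAP text not seen here already plans a between-arm analysis, the two places should be reconciled so that one rule governs the conclusion.

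The cost is SAP wording. The named software can produce these figures, and no new data, visits or participants are needed. The downside is that a significant change within one arm can no longer be the headline, and at pilot size the interval is likely to be wide.
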